6.2.8 Dose preparation

Personnel should use appropriate protective clothing and equipment during syringe filling and application to prevent contamination with the radioactive solution (medical gloves / protective glasses). The usage of shielded syringes is strongly recommended; however, this decision will be dictated by the individual guidelines of the respective nuclear medicine department. Filling of the syringe should take place in a safety bench or similar cabinet in the Radiopharmacy/ Nuclear Medicine department. The individual responsible for study drug preparation will draw the correct volume of study drug into a syringe. The size of the syringe should be chosen according to the applied volume to reach the required dosing accuracy. Ra-223 dichloride should not be diluted or mixed with any solutions. If the vials have been stored in a refrigerator, they should be left at room temperature for 1 hour prior to use, since cold material should not be injected in a patient.

6.2.9 Dose administration

Before administration of study drug, the patient must be well hydrated; the patient should be instructed to drink ad libitum. Aseptic technique should be used in the administration of Ra-223 dichloride. The syringe should be handed over to the individual who will perform the injection. The study medication will be administered as a slow bolus intravenous (IV) injection. After administration, the equipment used in connection with the preparation and administration of drug is to be treated as radioactive waste and should be disposed in accordance with hospital procedure for the handling of radioactive material. Written information about Ra-223 dichloride and instruction about handling and injection of radioactive material will be given to study personnel

Radiation Safety Considerations

Radiation Risk Management for Patients

Biodistribution of ^{223}Ra in the body

Pharmacokinetics, biodistribution and dosimetry in man have been previously investigated (see also ATI-BC-1: blood pharmacokinetics; BC1-05: pharmacokinetics, biodistribution and radiation dosimetry; Algeta ASA). After intravenous injection of ^{223}Ra dichloride, then radiopharmaceutical is quickly eliminated from blood, taken up in bone and excreted via the small intestine. The major route of elimination is through the gut with the feces; at 48 hours only 1-5% was excreted in urine and the rate of urinary excretion was decreasing. Thus, the kidneys, urinary bladder, and urethra are exposed to a minimal amount of radiation.

Gamma scintigraphy images show early activity in the gut, decreasing at the later images. It is not possible to determine the relative activity within gut wall versus gut contents from the scan, but it is assumed that the activity is mainly confined to the gut contents (i.e. fecal stream). This is a reasonable assumption since the activity in the scans is seen to move along the gut. No specific uptakes were seen in any other normal organs such as the heart, the liver, the kidney, the gallbladder, stomach and the spleen. The highest absorbed doses were measured in the bone with lesser amounts in the red marrow.

Biosampling (blood tests)

In the first week after injection of Ra-223 dichloride, there may be radioactivity in body fluids. A considerable fraction of the study drug is eliminated via feces, and to a lesser degree via urine. Blood clearance after injection is very rapid (<1% remaining 24 hours post injection). To ensure radiation protection for hospital personnel, special attention should be directed to ensure that only necessary samples of blood, urine and feces should be handled during the first week after administration. In case of necessary unforeseen blood samples, laboratory personnel should be notified in order to avoid contamination. All patients in clinical trials with Ra-223 dichloride receive a card stating that they have received a radioactive drug and that special care should be taken during unforeseen contact with medical or public health services.

Restrictions for patients

Unlike many other radiopharmaceuticals, there are no restrictions on family contact after administration of Ra-223 dichloride. The range of α -particles in human tissue is ≈ 0.1 mm. Once injected, both α - and β -particles emitted from Ra-223 are stopped by the patient's tissue. Due to attenuation in the patient's body mass, the radiation outside the patient's body is extremely low and there should be no safety issues related to homeland security/airport travel. Nevertheless patients should have a letter or card indicating recent treatment with a radioisotope in case of detection in by radiation detectors while traveling (advice: wear clean underpants!). Dose rates ($\mu\text{Sv/h}$ per MBq injected) measured outside the body are ~ 200 at one centimeter and 0.02 at one meter[16]

Ra-223 dichloride can be given on an out-patient basis, and there are no restrictions on normal interactions with friends or relations. Patients are provided with written instructions describing simple steps to be followed at home in connection with vomit, blood, urine or stools for a period of one week after dosing.

Burial and Cremation risks

After burial ^{223}Ra will decay naturally and has essentially no health risk to others after 3 months. Cremation of a body containing ^{223}Ra does not present a significant risk to the local population or to the crematorium workers themselves, even if the worst case scenarios are assumed. When crematorium workers receive a body that contains any type of radioactivity, they should be suitably trained, informed

beforehand and given suitable personal protection equipment (i.e. universal blood and body fluid precautions - especially when handling ashes containing potentially radioactive bone fragments. Calculations and the rationale for radiation dose estimates are available upon request (see investigators Brochure).

Definition of Dose-Limiting Toxicities (DLTs):

Toxicities will be graded in severity according to the guidelines outlined in the NCI Common Terminology Criteria for Adverse Events (CTCAE) version 4.0 (publish date 28-May-2009). Dose-limiting toxicities include all adverse experiences that are related to study medication, and clearly not related to disease progression or intercurrent illness.

Based on prior experience with other bone seeking radiopharmaceuticals and Ra-223 dichloride in prostate cancer patients, the expected dose limiting toxicity (DLT) will be hematologic. Lymphopenia is common in patients with bone metastases and will be monitored, but not considered a DLT in this protocol. Any grade 4 anemia, any grade 4 neutropenia for >7 days or grade 4 neutropenia with fever (a single temperature greater than 38.3°C or a sustained temperature of $\geq 38^\circ\text{C}$ for more than one hour) and grade 3 or 4 thrombocytopenia with clinically significant bleeding will be dose limiting. Grade 3 non-hematologic toxicities except for nausea, emesis or diarrhea that are controlled with maximal medical management within 72 hours will be considered dose-limiting. DLTs will only be monitored during the first 6 weeks of treatment. Ongoing toxicity that causes a delay of more than 2 weeks in starting the next cycle will also be dose-limiting if it occurs during the first cycle.

Dose Modification and Escalation

Every effort should be made to administer the full dosing regimen of Ra-223 dichloride. Adjustment of dose level is not permitted.

- A minimum of 3 patients initially will be enrolled at the first dose level.
- If at least 2 patients are observed to have a dose-limiting toxicity (DLT), the MTD will have been exceeded and no further patients will be enrolled at this dose level or at any higher dose level. The prior dose level is defined as the MTD (unless only 3 patients have been treated at that level, in which case it is the tentative MTD).
- If 0 of the 3 patients are observed to have DLT during the DLT assessment period, the dose level is escalated one step for the next cohort of 3 patients, and the process continues as above.

- If exactly 1 of the 3 patients treated show DLT during the DLT assessment period, 3 additional patients are treated at the current dose level.
- If none of these additional 3 patients show DLT during the DLT assessment period, the dose level is escalated for the next cohort of 3 patients, and the process continues as above; otherwise, the prior dose level is defined as the MTD (unless only 3 patients have been treated at that level, in which case it is the tentative MTD).
- A tentative MTD becomes final when a total of 6 patients are treated with less than 2 showing DLT.
- If 2 of the first 3 patients have hematologic DLT, then next cohort will be dose level -1.

Study visits during the treatment period should occur at 4 weeks intervals (within a window of +/- 7 days). **Dosing delays** may be instituted under the following circumstances:

Disease progression:

The Investigator should delay cytotoxic chemotherapy, other systemic radioisotope, hemibody external radiotherapy or other investigational drug until the follow-up period. If such treatments have to be given during the treatment period, further study drug administrations must be discontinued. Patients with disease progression may continue other treatment at the Investigator's discretion.

Myelosuppression:

Treatment-related changes in hematology parameters may occur.

- Blood transfusion is acceptable between study drug administrations. Use of biologic response modifiers, such as G-CSF or GM-CSF, is allowed in the management of acute toxicity.
- If myeloid growth factors are required for the management of acute toxicity this event should be considered a DLT.

Gastrointestinal events:

Diarrhea should be treated as per local practice. A further dose of study medication should not be given before diarrhea is recovered to CTCAE v4.03 Grade 2 or baseline levels.

Nausea or vomiting should be treated as per local practice. A further dose of study medication should not be given before nausea or vomiting is recovered to CTCAE v.4.03 Grade 2 or baseline levels.

For any grade 3 hematologic toxicity for >14 days, study drug administrations must be discontinued (grade 4 events of anemia and neutropenia >7 days are dose-limiting).

Spinal Cord Compression:

If the patient experiences spinal cord compression during the treatment period, the patient should be treated for the event, and this will be considered disease progression.

Surgical Intervention:

If surgery is required, the patient should continue with study treatment, if this is considered safe in the treating Investigator's opinion. The surgeon needs to be notified that the patient has been given radioactive drug, and needs to follow the guidelines for radioactive protection.

Non-pathological fractures:

For traumatic fractures in weight-bearing bones during treatment phase, the study drug administration should be delayed for 2-4 weeks from the time of fracture.

Pathological fractures:

Pathological fractures may occur as the result of either progressive disease or increased physical activity associated with significant pain palliation. Pathologic fractures are to be treated in a manner that attempts to maintain the best functional status and quality of life. Study treatment may continue as planned.

Any Other Toxicity: Local practice will apply.

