 - Aspartate aminotransferase (AST) and alanine aminotransferase (ALT) \leq 2.5 x ULN
 - Creatinine \leq 1.5 x ULN
 - Albumin > 25 g/L
- Willing and able to comply with the protocol, including follow-up visits and examinations

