6.2.1 Radium-223 dichloride

6.2.2 Treatments to be administered

Ra-223 dichloride will be administered as a slow bolus IV injection at intervals of every 4 weeks for up to 6 cycles.

- Dose (50, 75, or 100 kBq/kg) will be assigned in cohorts of 3 after study registration in CORE.
- Dose #1 should be given within 30 days of study registration
- At least 3 patients will be required to successfully complete 6 weeks of therapy before advancing to the next cohort.
- Patients will receive the same Ra-223-dichloride dose as dose #1 for all subsequent doses.
- Monthly dosing (q 4 weeks +/- 6 days) as slow iv bolus for up to a total of 6 doses
- Monthly doses will be delayed, but no more than 2 weeks from scheduled dose for any grade 3 hematologic toxicity.

Criteria for subsequent doses (i.e. doses 2-6):

- Hematologic Toxicity (if present): Hb, ANC, and platelets- resolved to grade 2 or less within 6 weeks of prior dose. Since lymphopenia may be chronic, this will not be a criteria for subsequent doses
- All toxicities must be resolved to grade 2 or less in order to begin subsequent cycles
- Performance status ECOG 0 to 2
- Alkaline phosphatase stable or improving at the discretion of the treating physician
- Not on oxygen
- Not pregnant
- After dose #3 and before dose #4: stable disease or better in indicator lesions as determined by quantitative nuclear medicine imaging (^{18}F FDG PET-CT, quantitative $^{99\text{m}}\text{Tc}$ -MDP SPECT/CT, or Na^{18}F PET/CT) or RECIST criteria on anatomic imaging (note: often osteosarcoma "indeterminate" lesions 1-9 mm remain stable or have minimal change depending on chest CT technique).
- Anatomic imaging (CT or MRI) of all sites of disease along with chest CT at baseline and restaging for all patients will be done to allow for assessment of RECIST progression.
- RECIST progression will determine progressive disease regardless of other imaging.

For the Phase I aspect of the protocol, prior to advancing/changing dose levels, a cohort summary must be completed and submitted to the Clinical Research Monitor in the IND Office.

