7.1.1 Tabulated overview

Table 4 summarizes required labs and imaging.

Table 4: **Ra-223 dichloride for Osteosarcoma: observations/monitoring**

Test/Procedure	Before entry	Doses 2-6	After dose 3+ imaging	1 month after dose (end of study± 7 days)
-----------------------	---------------------	------------------	----------------------------------	---

Physical exam (including vital signs and performance status+BPS [§])	X	X		X
CT/MRI Scans ⁺	X		X	X
Nuclear Scans*	X		X	X
CBC** w diff	X	X	X	X
Creatinine	X		X	X
Bilirubin	X		X	X
ALT	X		X	X
Alk Phos	X	X	X	X
HCG**	X	X		
OSTEO ¹	X	X	X	X
BONE ALK ²	X	X	X	X
CTX ³	X	X	X	X
Pathology	X			

Nuclear scans: *bone scan required, Other imaging of indicator lesion(s): best study or studies for quantitative comparison after dose 3 and after dose 6 (e.g. LD of bone forming lesion on CT/MRI, or SUV on ¹⁸FDG-PET-CT, or SPECT with ^{99m}Tc-MDP bone scan, or Na¹⁸F PET).

[§]Brief Pain Survey.

⁺Evaluations to include anatomic imaging (CT or MRI) of all sites of disease along with chest CT at baseline and restaging for all patients will be done to allow for assessment of RECIST progression. RECIST progression will determine progressive disease regardless of other imaging.

HCG: Urine pregnancy test must be done within 7 days prior to start of study drug and when applicable prior to every cycle. Note serum HCG can be a false positive marker occasionally in osteosarcoma. For patients with a positive test result, pregnancy will be excluded by ultrasound.

**CBC w/diff: CBC every 2 weeks (± 7 days) for the first 2 cycles, then monthly or more frequently as clinically indicated

1 Osteoclastin

2 Bone specific alkaline phosphatase

3 Serum CTX

Timing of assessments

Assessments are to be done monthly as indicated in table 4.

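### For a patient who continues dosing, no creatinine, bilirubin or ALT is scheduled inside the 6-week DLT window, so a symptomless grade 3 liver or renal event could go uncounted at the escalation decision (minor)

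*Combined protocol and SAP*

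**What the plan says.** **DLT definition (section 6.2.9).** "Grade 3 non-hematologic toxicities except for nausea, emesis or diarrhea that are controlled with maximal medical management within 72 hours will be considered dose-limiting". The window is explicit: "DLTs will only be monitored during the first 6 weeks of treatment". The plan's expectation is that "the expected dose limiting toxicity (DLT) will be hematologic". Grade 4 neutropenia counts if it lasts more than 7 days or comes with fever.

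**Escalation (section 6.2.9, Dose Modification and Escalation; section 6.2.2).** No DLT in 3 patients leads to the next level; one in 3 leads to three more patients. The next cohort can open once at least 3 patients have completed 6 weeks. Before each later dose, "All toxicities must be resolved to grade 2 or less in order to begin subsequent cycles".

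**Testing (sections 7.1 and 7.1.1).** "Table 4 summarizes required labs and imaging". In that table creatinine, bilirubin and ALT are marked before entry, after dose 3 and at end of study; their cells under Doses 2-6 are blank. AST is an eligibility test (section 5.1.1) but has no row. The timing note reads "Assessments are to be done monthly as indicated in table 4". CBC is due every 2 weeks (+/- 7 days) for the first two cycles; extra counts after a grade 3 or worse cytopenia are permitted, not required.

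**General duty (section 7.4.1).** Patients must be monitored for adverse events, and this includes laboratory tests. No schedule is given.

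**The concern.** A grade 3 rise in transaminases, bilirubin or creatinine can be symptomless, and then only a blood test shows it. The plan counts such an event as a DLT if it falls in the first 6 weeks, yet the schedule names no test that would show it in that time. The same gap affects re-treatment: grade 2 or less is required before dose 2, but no liver or renal result is scheduled on which to judge it.

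In cohorts of three, a single event changes the action from escalating to treating three more patients. An uncounted DLT can push only toward escalation, here up to 100 kBq/kg, twice the 50 kBq/kg of the phase III trial described in section 1.3.2. The cohort summary (section 6.2.2) and the review at each dose level (section 9.2) can use only results that were obtained.

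**Working it through.** The plan states no figure on this point, so there is none to reproduce. Day 0 is dose 1; the DLT window closes on day 42.

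1. **When chemistry is first scheduled on treatment.** The dosing interval is 28 +/- 6 days (section 6.2.2).
   - Dose 2: 28 +/- 6 = days 22 to 34.
   - Dose 3: earliest 2 x (28 - 6) = day 44; nominal 2 x 28 = day 56.
   - If the +/- 7 day visit window in section 6.2.9 were used instead, dose 3 could fall on 2 x (28 - 7) = day 42, but the draw still follows that dose.
   - Scheduled chemistry tests between baseline and day 42 for a patient who continues: 0. Doses given before the first one: 3 of 6. Baseline labs must be less than 30 days old at dose 1, so they may be up to 29 days old.

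2. **Exception.** The end-of-study column comes about one month after the last dose, +/- 7 days. A patient who stops after dose 1 would reach it by about 28 + 7 = day 35, inside the window. A patient who stops after dose 2 would reach it at 22 + 28 - 7 = day 43 at the earliest on the dosing window, just outside.

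3. **Are the blank cells meant?** They appear to be. The chemistry rows have the same pattern as the CT/MRI and nuclear scan rows, which are plainly not done at every dose. CBC, alkaline phosphatase and the bone markers keep their mark under Doses 2-6. The monthly timing note defers to the table, so it does not fill the cells.

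4. **Neutropenia duration (secondary).** Assume counts exactly 14 days apart, with the first count after onset falling uniformly in the 14-day interval. For an episode of D days, with results limited to 0-100%:

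| D (days) | Scheduled counts only: (D - 14)/14 | With a count on day 8 after the first grade 4 reading: (D - 8)/14 |
|---|---|---|
| 8 | 0% | 0% |
| 10 | 0% | 2/14 = 14% |
| 14 | 0% | 6/14 = 43% |
| 21 | 7/14 = 50% | 13/14 = 93% |

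   Entries are the chance that a duration above 7 days is established. A simulation that moves each scheduled count by up to 7 days, with onset spread evenly over days 7 to 28 (also assumed), gives about 0%, 1%, 8% and 38% for scheduled counts only. The week-6 CBC may fall on 42 +/- 7 = days 35 to 49, so it can come after the window closes.

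5. **What an escalation effect would need (illustration only).** With q the observed DLT rate, P(escalate) = (1 - q)^3 + 3q(1 - q)^5. For an assumed true rate of 1/3 this is 0.428. If 95% of DLTs were seen, q = 0.3167 and P = 0.461; if 90%, q = 0.300 and P = 0.494. These cases require 1.7 to 3.3 percentage points of unseen DLTs per patient. The documents give no figure for that share.

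**The case against.** The strongest reply is that safety chemistry is not absent. Section 7.4.1 makes laboratory monitoring mandatory, and section 6.2.2 makes recovery to grade 2 a condition of each dose, so a careful investigator would order these tests. The documents also point to a low yield: DLTs are expected to be hematologic, no specific liver or kidney uptake was seen and urinary excretion was 1-5% at 48 hours (section 6.2.9), and excretory organs showed no histological change in animals (section 1.3.1). A DLT must also be drug-related and clearly not due to progression. A lasting abnormality would appear at the draw after dose 3.

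Most of this stands, and it sets the severity. It does not close the gap. A general duty does not ensure a result by a given day, and an abnormality first found after dose 3 lies outside the DLT window and may be seen after the next cohort has opened.

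On neutropenia, the reply is that the next 2-weekly count is mandatory and that ANC must have "resolved to grade 2 or less within 6 weeks of prior dose". Fever, growth-factor use and a first-cycle delay of more than 2 weeks also make the event a DLT. Section 7.1 names grade 3 or worse neutropenia as a reason for extra counts and mentions an optional local count in the week before dosing. This also stands. What is left is an afebrile episode, not treated with growth factor, whose duration is not established.

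**Conclusion.** The point holds as a minor scheduling defect. A stated DLT criterion, and the re-treatment rule that depends on the same results, has no scheduled liver or renal measurement by day 42 in patients who continue dosing. This rests on calendar arithmetic and a reading of Table 4, not on any assumed event rate.

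A reader might infer three stronger things, and the documents support none of them.

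- That the plan requires no laboratory safety monitoring. Section 7.4.1 requires it; the timing is what is missing.
- That no patient can have chemistry inside the window. One who stops after dose 1 may.
- That escalation is materially biased or the MTD will be set too high. The shift from 43% to 46-49% rests on an assumed DLT rate and assumed detection, and the liver and renal evidence in the documents points to few such events.

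The neutropenia part is smaller still. The percentages depend on assumed episode lengths and onset. The documents give only an all-grade neutropenia rate of 4% against 1% at 50 kBq/kg in prostate cancer (section 1.3.2), with no grade 4 rate and nothing for osteosarcoma.

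**What to change.** 1. In Table 4, mark creatinine, bilirubin and ALT under Doses 2-6 and add an AST row with the same marks. Of the four, AST matters least, since ALT is already measured.
2. Add the same assays, with the CBC, at a week-6 draw taken on or before day 42 and before the cohort decision.
3. Minor addition in section 7.1: require, rather than permit, a repeat CBC after any grade 4 ANC in the DLT window, including a count on day 8 after the first grade 4 reading if it is still grade 4. Exact 7-day spacing would not show more than 7 days until day 14.

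The cost is a few routine assays. Blood is already drawn before dose 2 for alkaline phosphatase and bone markers. At week 6 only a CBC is due, so one extra tube may be needed. Slightly more events may be counted as DLTs. Item 3 helps mainly for episodes of about 14 days or longer and adds little for shorter ones.

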5.2 Withdrawal of subjects from study

5.2.1 Withdrawal

Subjects **must be withdrawn from the trial** (treatment and procedures) for the following reasons:

- Subject withdraws consent from study treatment and study procedures. A subject must be removed from the trial at his/her own request or at the request of his/her legally acceptable representative. At any time during the trial and without giving reasons, a subject may decline to participate further. The subject will not suffer any disadvantage as a result.
- Progressive disease and dose limiting toxicity (DLT)
- Subject is lost to follow-up.
- Death.

Subjects **may be** withdrawn from the study for the following reasons:

- The subject is non-compliant with study drug, trial procedures, or both; including the use of anti-cancer therapy not prescribed by the study protocol.
- Pregnancy. Pregnancy will be reported as an SAE. (Note: subjects who have been withdrawn from treatment with study drug because of pregnancy should not undergo CT scans [with contrast]/MRI or bone scans while pregnant.)
- If, in the investigator's opinion, continuation of the trial would be harmful to the subject's well-being.
- The development of a second cancer.
- Development of an intercurrent illness or situation which would, in the judgment of the investigator, significantly affect assessments of clinical status and trial endpoints.

- Deterioration of ECOG performance status to 4.
- Use of illicit drugs or other substances that may, in the opinion of the investigator, have a reasonable chance of contributing to toxicity or otherwise skewing trial result.

Any subject removed from the trial will remain under medical supervision until discharge or transfer is medically acceptable.

In all cases, the reason for withdrawal must be recorded in the CRF and in the subject's medical records.

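### No rule acts on DLT-free patients when their dose level is declared above the MTD, and the fixed-dose rules bar stepping them down

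*Combined protocol and SAP*

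**What the plan says.** Two rules fix each patient's dose. Section 6.2.2 states: "Patients will receive the same Ra-223-dichloride dose as dose #1 for all subsequent doses". Section 6.2.9, under Dose Modification and Escalation, states: "Every effort should be made to administer the full dosing regimen of Ra-223 dichloride. Adjustment of dose level is not permitted".

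When at least two patients at a level have a DLT, the MTD has been exceeded and "no further patients will be enrolled at this dose level or at any higher dose level". The prior level becomes the MTD, or the tentative MTD if only three patients were treated there. The safety monitoring rule in section 8.1 works in the same way for the expansion: more than two DLTs pause accrual while a decision is made on the expansion dose. Neither rule mentions patients already on treatment at the level concerned.

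The mandatory stops depend on the individual patient's course:
- Section 5.2.1 requires withdrawal for the patient's own DLT or progression.
- Section 6.2.2 sets criteria before each later dose, among them "All toxicities must be resolved to grade 2 or less in order to begin subsequent cycles", ECOG 0 to 2, no oxygen, and stable disease or better before dose 4.
- Section 6.2.9 adds: "For any grade 3 hematologic toxicity for >14 days, study drug administrations must be discontinued".

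The remaining provisions are discretionary or general:
- possible withdrawal if the investigator judges continuation harmful (5.2.1);
- a cohort summary to the IND Office before dose levels change (6.2.2);
- data review at each level (9.2);
- study termination if the risk-benefit ratio becomes unacceptable (10);
- deviation for an immediate hazard (11.1);
- updated consent information when important new information arises (11.2).

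**The concern.** Once a level is declared too toxic, the trial has named a lower dose that it regards as safer. A patient at the exceeded level who has had no DLT cannot receive that dose under the plan as written. The patient either continues at the dose just judged too toxic or comes off therapy, and section 5.1.1 enrols patients with no standard curative option.

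Most of the remaining doses also fall after the formal toxicity window: "DLTs will only be monitored during the first 6 weeks of treatment". Under section 7.1 the blood count goes from every two weeks to monthly after cycle 2, unless there is a clinical reason for more. This matters because the expected DLT is hematologic. A count is still scheduled with doses 2 to 6 in Table 4, so monitoring becomes lighter but does not stop.

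What is at stake is avoidable exposure in a few patients, not the validity of the dose-finding result.

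**Working it through.** **The plan's own figure.** Table 1 gives 3 + 3 + 8 = 14 in escalation, and 14 + 6 = 20, which matches the synopsis. This point disputes no stated number.

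**Doses remaining.** With on-time dosing every 4 weeks, doses fall at weeks 0, 4, 8, 12, 16 and 20.
- At the end of a patient's 6-week window, two have been given and 6 − 2 = 4 remain.
- If the second DLT is seen before a cohort-mate's dose 2, 6 − 1 = 5 remain. This is the maximum.
- In a level of six, first-group patients have 0 to 4 left, depending on accrual: 4 if the second DLT falls in their weeks 6 to 8, and none if the declaration comes after dose 6.

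**Extra activity.** Levels in Table 1 are 25 kBq/kg apart (25, 50, 75, 100). The excess over the prior level is therefore up to 4 × 25 = 100 kBq/kg, or 5 × 25 = 125 kBq/kg at the maximum. Stepping down after dose 2 would change the six-dose total as follows:
- 100 level: 2×100 + 4×75 = 500 instead of 600 (−17%)
- 75 level: 2×75 + 4×50 = 350 instead of 450 (−22%)
- 50 level: 2×50 + 4×25 = 200 instead of 300 (−33%)

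**Patients affected.** The documents give no DLT rates, so p = 0.1 to 0.5 is assumed, with independent patients. Let b_k be the Binomial(3, p) probability of k DLTs. A level is exceeded after 2 or 3 of 3, or after 1 of 3 followed by at least 1 of the next 3:

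P = b2 + b3 + b1(b1 + b2 + b3).

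The DLT-free counts on these paths are 1 (2 of 3), 0 (3 of 3), and 4, 3 or 2 (1 of 3, then 1, 2 or 3 of 3). If each group of three is fully enrolled, the expected count per tested level is

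U = b2 + b1(4b1 + 3b2 + 2b3),

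and the mean given that the level is exceeded is U/P.

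At p = 0.3: b1 = 0.441, b2 = 0.189, b3 = 0.027.
- P = 0.216 + 0.441 × 0.657 = 0.506
- U = 0.189 + 0.441 × 2.385 = 1.241
- U/P = 2.45

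| p | P (exceeded) | Mean DLT-free if exceeded | Per tested level (U) | Chance of at least one, if exceeded |
|---|---|---|---|---|
| 0.1 | 0.09 | 3.0 | 0.28 | 99% |
| 0.2 | 0.29 | 2.8 | 0.80 | 97% |
| 0.3 | 0.51 | 2.5 | 1.24 | 95% |
| 0.4 | 0.69 | 2.1 | 1.46 | 91% |
| 0.5 | 0.83 | 1.8 | 1.45 | 85% |

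These are upper bounds. If the additional three are enrolled one at a time and enrolment stops at the second DLT, the conditional means fall to 2.3, 2.2, 2.0, 1.7 and 1.5. Progression and other withdrawals lower them further.

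**Expansion.** A third DLT among six expansion patients leaves up to 3 who are DLT-free, plus any escalation patients still on that dose.

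**The case against.** The strongest reply is that keeping a patient on a dose that the patient tolerates, with toxicity checked before every cycle, is a defensible choice. This stands, and it argues against making step-down compulsory. So does activity: section 4 reports ALP normalization in a prostate cancer phase II study in 17% of patients at 25 kBq/kg and 40% at 50 kBq/kg, so moving from 50 to 25 could cost benefit.

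It can also be said that the patient is not left uninformed or without a route. Section 11.2 requires that important new information reach the patient, who may then stop. Section 11.1 allows a protocol change with Bayer's agreement. Both stand, but section 11.2 asks only for timely information, with no deadline before the next dose, and an amendment is not a routine step-down. The cohort summary in section 6.2.2 is mandatory oversight, yet it prescribes nothing for patients on treatment. The dose-reduced category in the adverse event form (7.4.1.2.4) does not override the explicit bar.

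The conditional counts are also largest at p = 0.1, where the declaration is most likely a false alarm. That is fair, and it is why the unconditional column is shown.

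Two stronger readings are not supported. A reader might infer that only discretionary withdrawal can stop these patients, but the mandatory individual stops can each stop a patient who has had no DLT. A reader might also take the 8 planned at 100 kBq/kg in Table 1 and conclude that two DLTs would leave six patients exposed, but the 3+3 rules treat three or six per level.

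**Conclusion.** The gap is real and limited. Neither an exceeded-MTD declaration nor a decision to de-escalate the expansion triggers any action for DLT-free patients already on that dose, and the fixed-dose rules both hold them there and bar the step down. The count rests on the assumed DLT rates, independence and full enrolment of each group. On those terms an exceeded level leaves on average at most about two to three such patients, each with typically up to four doses to come.

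A reader might infer that the MTD itself is compromised. It is not, because the decision uses only the first 6 weeks, before any of this exposure matters. Nor do the documents show that continuing is wrong for every such patient. The plan should permit stepping down and require an explicit decision. This is a cheap improvement in patient protection, not a flaw in the dose-finding logic.

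**What to change.** In section 6.2.9, Dose Modification and Escalation, qualify the bar on adjusting dose level with one exception:

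> except that when a level is declared above the MTD, or the expansion review decides to de-escalate, each patient still on that level is informed before the next dose, and the investigator documents a benefit-risk decision, with the patient's agreement, to continue at that level, to step down to the prior dose level, or to stop.

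Then:
- Cross-refer to this exception from the same-dose rule in section 6.2.2.
- Beside the rule that "A tentative MTD becomes final when a total of 6 patients are treated with less than 2 showing DLT", state that stepped-down patients do not count toward those six.
- In section 8.1, analyse stepped-down patients under their starting level up to their last dose there, and list later data separately.

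The change needs no extra patients or visits. It does have costs:
- There would be fewer full-course safety data at the exceeded level, which bears on the primary comparison of 50, 75 and 100 kBq/kg.
- There would be fewer full-course ALP and imaging data for the secondary objective.
- Activity may be lost if a patient steps from 50 to 25 kBq/kg.
- The amendment needs IRB approval and Bayer's agreement, with a matching sentence in the consent form.
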